#### 4. Analysis

**Describe any qualitative tests and measures as well as quantitative methods:**

Our primary outcomes of interest will be  $\Delta$  first fixation duration to peripheral cues,  $\Delta$  cumulative fixation to peripheral cues, and  $\Delta$ EAH and our primary exposures will be the multi-task vs. control condition and the sustained attention task vs. control. We will first assess main effects of the acute tasks by using multivariable linear regression to fit  $\Delta$  attention eye-tracking metrics on  $\Delta$ EAH. Cohen's power calculation for regression, and setting alpha to  $P < .05$ , two-tailed, we calculated 80% power to detect a moderate effect size ( $f^2 = .15$ ) for main effects. To test for moderation, we will then repeat the main effects models stratifying the sample by the median of usual media multi-tasking. We will conduct a formal test for interaction by repeating the main effects models on the entire sample with the acute task, usual media multi-tasking, and the product of the acute task and usual media multi-tasking as the independent variables of interest. A Wald test on the product term  $P < 0.10$  will be considered evidence of a statistically significant interaction.

To examine the effects related specifically to food images, we will repeat all analyses using first fixation bias and cumulative fixation bias to food cues as our outcomes of interest. A first fixation bias to food cues was calculated by computing the difference between first fixation duration to food and animal images. A positive value represents that a child looked longer the first time they fixated a food versus toy distractor. A cumulative gaze duration bias to food cues was calculated by computing difference between cumulative fixation duration to food versus toy animal distractors. A positive number indicates that a child spent more total time looking at food versus toy distractors.

We assessed power to detect a significant correlation between each predictor and our outcome using Cohen's method for Pearson's correlation coefficient (74). Using 107 participants (assuming a retention rate of 85%), 80% power, and a Type I error rate of 0.05 (two-tailed), we calculated that Aim 1 is powered to detect a moderate effect size of  $|r \geq 0.27|$  for either predictor with EAH. Cross referencing this effect size and our power analysis parameters with the empirical power tables for mediation created by Fritz and Mackinnon (75), we found that that our study is 80% powered to detect if media multi-tasking fully mediates the relationship between attention to food cues and EAH.

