## APPROACH

### Main Study

We will achieve our aims by having 13-17-year-olds visit the laboratory on three occasions to complete each of three tasks: a media multi-tasking paradigm, an eye-tracking task that measures attention to food cues, and an EAH paradigm. Additionally, children will complete a questionnaire-based media multi-tasking scale. Children will be randomized to complete the multi-task, sustained attention, or control condition of the media multi-tasking paradigm during their first visit and will complete the alternate conditions during their second and third visits. The experimental flow for individual laboratory visits is shown in Figure 2.

**Preload meal.** In order to control for satiety, children will be fed a standardized palatable dinner at the beginning of the study using established methods (48).

**Multi-tasking experimental manipulation.** Immediately following dinner, children will complete one of three conditions (attentional training, acute media multitask, or control) in a modified version of the Go/No-go task to simulate media-multitasking.

**Attentional training.** A Go/No-go task was used to train sustained attention. For the task, a blue or yellow dot briefly appeared for between 20 - 1500 msec and then disappeared. Participants were instructed to respond to the blue dot by pressing the space bar as quickly as possible (Go trials) and were told not to respond when presented with a yellow dot (No-go trials). At random intervals between 2000 – 5000 msec the messaging bot would ding and send participants a text message. The text message included questions about random facts; for example, how many teeth does an alligator have? Participants were instructed to ignore the messages and focus on the Go/No-go task. By asking participants to practice ignoring incoming messages and focus on a task designed to increase sustained attention, the training condition was designed to reduce acute media multitasking and increase sustained attention. Participants completed 100 Go trials and 100 No-go trials randomized on a trial-to-trial basis. There was a total of 60 messages sent to participants.

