**Attention to peripheral cues.** Immediately following the multi-tasking experimental manipulation, children will play a game of Tetris that measures attention to peripheral cues using eye-tracking. On either side of the game screen are pictures of food and animals that change periodically. Study staff will set up children with the task, provide directions, have children do a practice trial game, and clarify directions if necessary. The food cue is chosen at random on a game-to-game basis. To encourage gameplay concentration, children are encouraged to complete as many games as possible within 10 minutes. This game has high ecological validity because it mimics Internet advergames that are used to advertise products to children (2). We will use established eye-tracking metrics to measure attention to food cues. The amount of attention given to peripheral cues while playing the video game Tetris will be calculated for each participant after they completed each experimental condition. Areas of interest will be created around distractor images, defined as the area of the image, 250 X 250 pixels. First fixation duration will be measured as the average amount of time an adolescent spent fixating a distractor the first time that they looked at it. Cumulative fixation duration will be calculated as the total amount of time participants spent fixating distractors, summed over all fixations. For both measures, a fixation duration will be defined as any stationary period lasting at least 100 milliseconds. Eye-tracking will be recorded using the EyeLink 1000 Plus (SR Research, Ottawa, Ontario, Canada). The EyeLink is a robust desktop configuration that also includes facial recognition software to monitor head movements. This ability to compensate for head movements is particularly useful because it assures that when participants look away from the stimulus and then return to it, the system will automatically reacquire the eye. Critically, the video used to track the eyes is not saved and the person's likeness is never recorded.

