## 11. Informed Consent, Assent, and Authorization

**All forms discussed in this section should be uploaded to the ‘Consent Forms and Recruitment Materials’ page in Rapport**

**a. Please describe the consent and/or assent process, addressing the following:**

- Who will obtain consent/assent from participants
- Where the consent/assent process will take place
- The timeframe for providing information potential participants about a study, having the consent form signed, and beginning study activities
- Any precautions taken to minimize the possibility of coercion or undue influence

- The forms which will be used as well as any aids used to simplify scientific or technical information
- How comprehension will be ensured

When a parent first contacts the study to express interest in having his/her child participate in the study, a thorough screening interview will be conducted over the phone, at which time the study procedure will be described in detail (including financial compensation). When the child (and parent) visit the lab for their study appointment, trained research staff will explain the study in plain language and obtain electronic written consent from the parent and electronic written assent from the child, both via REDCap. The study will be promoted to the child as a study to understand how exposure to multi-media types influences children; specific study goals will be concealed to prevent biasing participant behavior. It will be emphasized that the child can choose to stop participating in the study at any time. Parents of children will be told the true nature of the study prior to providing consent for their child's participation so that they can make an informed decision.

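### Differencing against one control visit drops children who leave before it and is biased if outcome-related leaving differs by first condition; a mixed model on all attended visits avoids this

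*Combined protocol and SAP*

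**What the plan says.** The design is a three-visit crossover with one condition per visit. Under Main Study: "Children will be randomized to complete the multi-task, sustained attention, or control condition of the media multi-tasking paradigm during their first visit". The other two conditions follow at visits 2 and 3, in an order that is not specified.

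Gaze "will be calculated for each participant after they completed each experimental condition". Snack intake is obtained once per visit, by weighing the food before and after. No within-visit baseline is described for either measure.

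Section 4 takes the change in first fixation, in cumulative fixation and in eating in the absence of hunger (EAH) as primary outcomes, and states that "our primary exposures will be the multi-task vs. control condition and the sustained attention task vs. control". The main-effects analysis uses "multivariable linear regression to fit" these change scores.

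Loss is expected. The power paragraph reads "Using 107 participants (assuming a retention rate of 85%), 80% power, and a Type I error rate of 0.05 (two-tailed", and section 11 stresses that "the child can choose to stop participating in the study at any time". No missing-data method, analysis set, mixed model or rule for children with one or two visits is given. Section 5 allows data thought inaccurate to be excluded and logs completion rates, but not by condition. Visit order is not among the potential covariates listed in section 3.

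**The concern.** One control visit serves both contrasts, so missing it removes the child from both. Whatever such a child contributed at the task visits goes unused.

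The children left in a difference analysis are also selected. If, say, light eaters tended to leave after a control-first visit but not after a task-first visit, the control values among those who remain would be shifted upward, and both task-minus-control differences downward. For the training contrast that is the hypothesised direction.

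The conditions do differ in burden: one is passive viewing, another requires typed answers to 60 messages alongside a reaction task. Unequal leaving is therefore plausible, although the documents give no evidence that it will occur.

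**Working it through.** **The plan's own figure.** For a Pearson correlation, n = ((1.960 + 0.842)/atanh(r))² + 3. With r = 0.27, atanh(r) = 0.277 and n = 106. With n = 107 the smallest detectable r is 0.268, and power at r = 0.27 is 80.6%. The stated 0.27 reproduces.

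**Inputs.** From the documents: three visits, first condition randomised, 15% loss, and 120 children (section 9). Assumed: the change score is task minus control; six equally likely orders; within-child correlation ρ of 0.3 to 0.7; the timing of leaving. Results are in units of the single-visit outcome SD.

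**Who is lost.** Leavers = 0.15 × 120 = 18. After visit 1, one third have attended control. After visit 2, two thirds have.

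| Timing of leaving | Leavers without control | Leavers giving one difference | Differences per contrast |
|---|---|---|---|
| All after visit 1 | 12 | 0 | 102 |
| Half after each visit | 6 + 3 = 9 | 6 | 102 + 3 = 105 |
| All after visit 2 | 6 | 12 | 102 + 6 = 108 |

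In the last row, 12 × 2 = 24 of the 36 visits attended by leavers remain usable.

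**Precision.** The SE of a contrast from n differences is √(2(1 − ρ)/n). At ρ = 0.5 this is √(1/102) = 0.0990 for the first row and √(1/108) = 0.0962 for the last. A mixed model on all attended visits gives 0.0976 and 0.0945. The variance ratios are 1.029 and 1.037. Across ρ = 0.3 to 0.7 and all three timings the ratio runs from 1.018 to 1.043. A separate simulation gave 1.01 to 1.05.

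**Bias from selective leaving, no true effect.** Suppose leaving occurs after visit 1. Let p be the fraction retained in each first-condition group, and a the shift in mean first-visit outcome among those retained. In a multi-task-first child, the multi-task value shifts by a and the control value by ρa. The reverse holds for control-first children. In training-first children both shift by ρa and cancel. So, with M, S and C for multi-task-, training- and control-first:

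bias (multi-task minus control) = (1 − ρ)(p_M a_M − p_C a_C)/(p_M + p_S + p_C).

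- Same dependence on the first outcome in every group: p_M a_M = p_C a_C, so the bias is zero. Random leaving, or leaving that depends only on the first condition, makes every a zero, so the bias is again zero.
- The highest 45% of multi-task-first children leave (15% overall): p_M a_M = −φ(0.126) = −0.396, and the retained fractions sum to 2.55. At ρ = 0.5 the bias is 0.5 × (−0.396)/2.55 = −0.078. Large-sample simulation gave −0.107, −0.076 and −0.046 at ρ = 0.3, 0.5 and 0.7.
- The highest 30%, 10% and 5% leave in the multi-task-, training- and control-first groups: at ρ = 0.5 the bias is −0.5 × (0.348 − 0.103)/2.55 = −0.048. Simulation gave −0.066, −0.047 and −0.028.
- Milder case, by simulation: 126 enrolled, about 15% leaving (half after each of visits 1 and 2), light eaters leaving after a control-first visit, leaving otherwise random. Training minus control was biased by −0.022 and −0.021 at ρ = 0.4 and 0.6 using any child with the pair, and by −0.032 and −0.028 using three-visit completers only.

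In all these cases the mixed model was within 0.005 SD of the truth.

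**Bias from a trend over visits.** Assume a fall of 0.3 SD per visit and a random 45% of control-first children leaving after visit 1. The other visits average −0.45 relative to visit 1, so multi-task minus control averages −0.45 in control-first, +0.45 in multi-task-first and 0 in training-first children. The weighted mean is (0.45 − 0.55 × 0.45)/2.55 = +0.08 SD, with no outcome-related leaving at all. With this trend and differential leaving, a random-intercept model without a visit term was biased by +0.02 to +0.06 SD. Adding visit brought it to about 0.

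**The case against.** The strongest reply is that the effect is small and the mechanism hypothetical. In the milder case a bias of 0.02 to 0.03 SD, against an SE of about 0.0976, is 0.2 to 0.3 of one standard error. The figures near 0.1 SD need heavy selection, such as 45% of one group leaving from the top of the distribution. Snack intake is measured without the child's knowledge, so the amount eaten gives no stated reason to leave. Payment rises from $30 to $40 to $70 across visits, which favours retention. If 150 are enrolled, 85% retention leaves about 127, above the 107 used for power. All of this stands, and it limits the size of the point.

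Three stronger readings are tempting but unsupported.

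- A reader might infer that every leaver's visits are wasted. That would require a three-visit-completer rule, which the documents neither state nor exclude. Otherwise a two-visit child with control still gives one difference.
- A reader might infer that any leaving linked to the first session causes bias, or that the difference analysis is valid only when leaving is unrelated to the first outcome within each condition. The algebra shows cancellation when the dependence is equal across conditions.
- A reader might infer that any mixed model is a safe replacement. Without a visit term it can itself be biased.

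The reply does not remove the gap. The plan expects loss, yet leaves the use of partial completers open for three outcomes and two contrasts.

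**Conclusion.** The point holds in a limited form. On the reasonable but unstated reading of the change score, children who leave before control drop out of both contrasts, and the difference analysis is exposed to bias when outcome-related leaving differs by first condition, or when leaving differs by first condition and outcomes drift over visits. The plausible size is 0.02 to 0.1 SD. This rests on assumed leaving patterns, balanced orders and within-child correlations of 0.3 to 0.7, none of which the documents supply. Lost precision alone would not justify a change. Validity under a weaker assumption about leaving does. The change should be made, but the plan is not invalid without it.

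**What to change.** - Define the change score explicitly.
- As primary analysis, fit a repeated-measures mixed model to EAH, first fixation and cumulative fixation from every attended visit of every randomised child, including those who withdraw. Use fixed effects for condition, visit (period) and sequence, and a child random intercept. Take each task-minus-control contrast from that model.
- Keep the difference analysis, in children with both visits, as a sensitivity analysis.
- Report withdrawals by first condition and by last attended condition.

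This changes the analysis text and one report table. It needs no new visits, data or participants. The costs are slightly more modelling and reliance on data being missing at random given what was observed, which should be stated as an assumption.

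### The model given for the task main effects regresses one primary outcome on another, with no condition term, so it estimates neither task-versus-control contrast

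*Combined protocol and SAP*

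**What the plan says.** Section 4 (Analysis) lists three primary outcomes: Δ first fixation duration, Δ cumulative fixation and ΔEAH. It then states that "our primary exposures will be the multi-task vs. control condition and the sustained attention task vs. control". The next sentence gives the model: "We will first assess main effects of the acute tasks by using multivariable linear regression to fit". The left-hand side that it goes on to name is the set of Δ eye-tracking measures, and the right-hand side is ΔEAH; the linking words are "attention eye-tracking metrics on". The power statement follows directly: "we calculated 80% power to detect a moderate effect size", with f² = .15.

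Later analyses are defined by reference to that model:

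- Moderation: "To test for moderation, we will then repeat the main effects models stratifying the sample by the median of usual media multi-tasking".
- Interaction: "repeating the main effects models on the entire sample with the acute task, usual media multi-tasking, and the product of the acute task"; the other factor in that product is the usual multi-tasking score. This is the only place where a task variable is named as a model term.
- Food images: "we will repeat all analyses using first fixation bias and cumulative fixation bias to food cues as our outcomes of interest".

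Δ is not defined. The paragraph on attention to peripheral cues (Approach, Main Study) says that attention "will be calculated for each participant after they completed each experimental condition". Section 3 describes three visits, with each child completing all three conditions.

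**The concern.** The sentence offered as the test of the acute tasks has a declared primary outcome on each side and neither declared exposure. It tests whether children whose attention changed more also ate more. It does not test whether either task changed attention or eating. The association is part of the pathway in Section 2 and is worth analysing, but it is not the task effect.

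The design has each child complete all three conditions, with the starting condition randomised, in order to obtain within-child task-versus-control contrasts. Followed literally, the plan leaves both contrasts unestimated on all three primary outcomes. The stratified and food-image analyses repeat the same model and carry the same fault. The second power paragraph of Section 4 treats EAH as the outcome, whereas the model sentence puts it on the right-hand side, so even the direction of the regression is unsettled.

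**Working it through.** **Inputs.** From the documents: n = 107, 85% retention, 80% power, two-sided 0.05, |r| ≥ 0.27 and f² = .15 (all Section 4). Assumed: Δ is task minus control within child, with one regression per contrast; shifts are in SD units of the within-child difference; correlations are as shown. The documents give no SDs or expected task effects.

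**1. The plan's own figure.** Smallest detectable correlation: tanh[(1.960 + 0.842)/√(107 − 3)] = tanh(0.2747) = 0.268. Power at r = 0.27 is 80.6%. The stated figure reproduces, but it is power for a correlation, not for a condition contrast. The f² = .15 sentence gives neither n nor the number of predictors. At n = 107 its power is 97.8% with one predictor, 95.2% with two and about 79.5% with eight.

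**2. Algebra.** Let A be Δ attention and E be ΔEAH. The task effects are mean(A) and mean(E). The fitted slope is b = Σ(E − Ē)(A − Ā)/Σ(E − Ē)². Adding a constant to A, to E or to both leaves every deviation, and so b, unchanged. Further covariates do not alter this, because the intercept absorbs the constants. The intercept is Ā − bĒ. It equals the attention contrast only if b or Ē is zero.

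**3. Simulation at n = 107** (20,000 trials per row, no covariates, unit SD; percentages are two-sided rejections at 0.05):

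| Correlation | Shift in A | Shift in E | Mean slope | Slope rejects | Mean intercept | Intercept rejects | Test of mean A rejects |
|---|---|---|---|---|---|---|---|
| 0 | 0.28 | 0.28 | 0.00 | 4.9% | 0.28 | 79% | 82% |
| 0 | 0.5 | 0.5 | 0.00 | 5.0% | 0.50 | 99.5% | 99.9% |
| 0.27 | 0 | 0 | 0.27 | 80.9% | 0.00 | 5.0% | 5% |
| 0.27 | 0.5 | 0.5 | 0.27 | 81.1% | 0.37 | 93% | 99.9% |
| 0.27 | −0.5 | 0.5 | 0.27 | 80.8% | −0.63 | over 99.9% | 99.9% |
| 0.27 | 0 | 0.5 | 0.27 | about 81% | −0.135 | about 25% | 5% |
| 0.4 | 0.2 | 0.5 | 0.40 | about 99% | 0.00 | about 5% | 53% |

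The slope is 0.27 whether there is no effect, effects in the same direction or effects in opposite directions. With five unrelated covariates, the slope rejection rates in the first two rows are 5.3% and 5.1%.

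The last two rows show how the intercept fails. By hand: 0 − 0.27 × 0.5 = −0.135, an apparent attention effect where there is none; and 0.2 − 0.4 × 0.5 = 0, a real effect cancelled.

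**4. Median-split half** (107/2, taken as 53). With uncorrelated deltas both shifted 0.5 SD, the slope rejects 5.0% and the mean-Δ test 95%. With no task effect and correlation 0.27, the slope rejects 51%.

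**5. Alternative reading: both contrasts stacked in one regression.** If multi-tasking alone raises both outcomes by 1 SD, the two row means are 1 and 0, which adds 0.25 to the covariance and to the variance of E. The slope is 0.25/(1 + 0.25) = 0.20. If training alone lowers both by 1 SD, the row means are 0 and −1 and the slope is again 0.20. Simulation gives 0.202 and 0.201. The slope reflects the difference between tasks and identifies neither contrast with control.

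**6. Scale for a direct contrast.** A paired t test at n = 107 has 80% power for a mean difference of 0.273 SD of the within-child difference, unadjusted for multiple tests.

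**The case against.** The strongest reply is that this is a drafting slip with recoverable intent. The preceding sentence names both contrasts, the regression is called multivariable without a full list of terms, and the interaction model includes the acute task. That probably does show what was meant. It does not supply the model: the interaction analysis is itself defined as a repeat of the main-effects models, and with a product term the task coefficient is the effect at a usual multi-tasking score of zero, not a main effect.

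A second reply is that if Δ is task minus control, the intercept carries the attention effect, so comparing only the slope with a direct test is too harsh. This stands in part. When the deltas are uncorrelated the intercept performs nearly as well as the direct test. When they are correlated it is biased and can show a false effect or hide a true one. It gives nothing for ΔEAH, and the plan does not say that it would be tested.

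Three smaller points also stand. The simulated sizes rest on assumed shifts and correlations, so they illustrate an algebraic fact and do not measure the error in this trial. An f² of .15 is generic and could be applied to a condition term. The documents do not say that the open choices would be made after the data are seen; they only fail to fix them beforehand.

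**Conclusion.** The concern holds. As written, the main-effects step estimates neither task-versus-control contrast on any of the three primary outcomes. The slope's indifference to the task effect is exact when Δ is task minus control and each contrast has its own regression. Under the stacked reading the slope still does not identify either contrast. That reading of Δ is an inference from the attention paragraph, since Δ is undefined and the flow figure is not available in the text reviewed. Under the stated assumptions the slope can be significant in about 81% of trials with no task effect, and in about 5% with a 0.5 SD effect on both outcomes. This needs correcting before analysis because it is the only statement of the main-effects model, and later analyses repeat it.

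**What to change.** - Define Δ explicitly: which condition is subtracted from which, and for which measures.
- For each primary outcome (first fixation, cumulative fixation, EAH in kcal), state a main-effects model with that outcome as the dependent variable and condition as the exposure, and report both contrasts with control. A mixed model over the three visits with condition, visit and a random child effect would do; so would a one-sample test of the mean within-child difference.
- Say that the stratified, interaction and food-image analyses repeat that model.
- List the attention–EAH regression separately as a secondary or mediation analysis, with its direction stated.
- Restate the main-effects power for the contrasts to be tested, giving n and the assumed difference. For scale, 107 children give 80% power for 0.273 SD of the within-child difference.

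The cost is a rewritten model sentence and power sentence in Section 4 and one added definition. No new data, visits or participants are required.

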
## 2. Objectives and Hypotheses

[figure not shown]
Our long-term goal is to understand the determinants of children’s individual susceptibility to environmental food cues and cued eating to develop interventions that reduce childhood obesity. Our overall objective is to determine how media multi-tasking affects attention to peripheral food cues and overeating, and whether it is possible to intervene on this proposed pathway. We have two central hypotheses. The first is that engaging in media multi-tasking increases attention to peripheral cues and thereby makes children more susceptible to environmental food cues (e.g., food advertising, sight or smell of food) that leads to cued eating in the absence of hunger. The second is that attentional training that improves sustained attention protects children against attention to peripheral food cues and therefore makes them less susceptible to cued eating.

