## 3. Study Design

**Describe all study procedures, materials, and methods of data collection:**

We will achieve our aims by having 13-17-year-olds visit the laboratory on three occasions to complete each of three tasks: a media multi-tasking paradigm, an eye-tracking task that measures attention to food cues, and an EAH paradigm. Additionally, children will complete a questionnaire-based media multi-tasking scale.

Children will be randomized to complete the multi-task, sustained attention, or control condition of the media multi-tasking paradigm during their first visit and will complete the alternate conditions during their second and third visits. The experimental flow for individual laboratory visits is shown in **Figure 2**.

[figure not shown]

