**Eating in the absence of hunger (EAH) measurement.** When the child finishes the memory game, he/she will be asked to "wait in the room" for 10 minutes while the experimenter allegedly takes care of tasks in a different room. During this period, the waiting room will contain pre-weighed snack items and games to measure EAH using established methods (1,58). The pre- and post-weights of each snack item will be used to calculate the number of kCal the child consumed. The EAH phase will take place within 20 minutes of the standardized dinner.

**Assessing usual media multi-tasking.** Children will complete the media multi-tasking index (MMI) (8). This index asks about media multitasking with other print and digital media during four primary activities: 1) watching TV or movies, 2) playing video games, 3) reading books or magazines (not assigned for school), and 4) doing homework. For each activity, participants reported the frequency with which they multitasked by engaging in the other activities by using a 5-point likert scale (i.e., 0=Never, 1=Rarely, 2=Sometimes, 3=Often, 4=Always). A usual media multitasking score was computed by taking the average of the Likert response. The score ranges from 0 to 4 with a higher score indicative of higher self-reported usual media multitasking, on cognitive control tasks (8,59,60).

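### The formal interaction test names a product term that does not fit the plan's change-score outcomes and three-condition within-child design

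*Combined protocol and SAP*

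**What the plan says.** Section 4 (Analysis) makes the primary outcomes changes (deltas) in first fixation duration, cumulative fixation and eating in the absence of hunger. It adds that "our primary exposures will be the multi-task vs. control condition and the sustained attention task vs. control". The model class comes from the next sentence: "We will first assess main effects of the acute tasks by using multivariable linear regression to fit" the attention deltas on the eating delta. Moderation is then examined in two ways. The first is descriptive: "To test for moderation, we will then repeat the main effects models stratifying the sample by the median of usual media multi-tasking". The second is the formal test, which refits the same models to all children using three terms: "the acute task, usual media multi-tasking, and the product of the acute task and usual media multi-tasking as the independent variables of interest". An interaction is declared when the Wald P value for the product falls below 0.10.

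Section 3 (Study Design) randomises each child to a first condition, after which the child "will complete the alternate conditions during their second and third visits". Under Approach, Main Study, the attention measure "will be calculated for each participant after they completed each experimental condition", so a delta can sensibly only be a difference between conditions. The moderator is one number per child: "A usual media multitasking score was computed by taking the average of the Likert response".

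The plan does not define delta, the number of rows per child or the coding of acute task. It names no child term, random effect or clustered standard error.

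**The concern.** A task-minus-control delta already contains the task contrast. In a model for that delta, moderation by usual multi-tasking is the slope on usual multi-tasking, and no product is needed. The plan nevertheless names the product as the quantity to test. That wording belongs to a model with separate rows for task and control, and the plan neither describes those rows nor allows for several rows coming from one child.

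This is the plan's only formal test of whether usual multi-tasking changes the task effects. Two analysts following the text could report no estimate, a comparison the plan does not list, or an underpowered test of the right comparison, all from the same data.

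**Working it through.** **Inputs from the documents.** Three conditions per child (section 3); one usual multi-tasking score M per child (Approach, Main Study); two contrasts with control and a Wald test at P<0.10 (section 4); 107 analysed children (section 4, power paragraph).

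**Inputs assumed.** The within-child correlation rho between conditions is not in the documents, so 0.3, 0.5 and 0.7 are shown. Variances are taken as equal across conditions, with the same rho for every pair, unless stated.

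**The plan's own figure.** No power is given for the interaction test. The nearest figure is a detectable |r| of 0.27 at N = 107, 80% power and two-sided 0.05. By Fisher's z, r = tanh((1.960 + 0.842)/√104) = tanh(0.275) = 0.268, so it reproduces. It supplies the sample size but says nothing about the product term.

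**Set-up.** Write the outcome under condition c as Y_c = a_c + b_c·M + e_c, with c = 0 (control), m (multi-task) or s (sustained attention). The moderation effects of interest are b_m − b_0 and b_s − b_0.

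**Reading 1: one delta per child, one model per contrast.**
- Y_m − Y_0 = (a_m − a_0) + (b_m − b_0)·M + error.
- The four columns are intercept, task (constant at 1), M and task × M (equal to M). Their rank is 2 of 4, so the product has no coefficient of its own.
- Once the aliased columns are removed, the slope on M is b_m − b_0, the wanted quantity. In simulation at n = 107 this slope rejected 9.8% to 10.7% of the time at nominal 10%, for rho from 0 to 0.7.

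**Reading 2: both deltas stacked, with acute task saying which delta.**
- The product estimates (b_m − b_0) − (b_s − b_0) = b_m − b_s. Control cancels.
- The two deltas share the control value and so correlate at 0.5. Ordinary regression ignores this and overstates the standard error by √2. The true level is 2·P(Z > 1.645·√2) = 2·P(Z > 2.326) = 2.0%.
- That 2.0% needs equal variances. If the multi-task SD is 1.5 times the others, the level is 3.8% to 4.2% over the three rho values.
- If both tasks are moderated equally, b_m − b_s = 0 and the product rejects only at its own level. Clustered errors would restore 10% but would not change the target.

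**Reading 3: undifferenced visit rows, control as reference, no within-child term.**
- The product estimates b_m − b_0, the right contrast.
- Its true variance is proportional to 2(1 − rho), while ordinary regression uses 2. The standard error is too large by 1/√(1 − rho).
- Benchmark effect: the one that the delta regression in reading 1 detects with 80% power at P<0.10, a standardised size of 1.645 + 0.842, or 2.486 before rounding.
- Level = 2·P(Z > 1.645/√(1 − rho)). Power = P(Z > 1.645/√(1 − rho) − 2.486).

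| rho | SE ratio | Critical value | Level at nominal 10% | Power (delta regression: 80%) |
|---|---|---|---|---|
| 0 | 1.00 | 1.645 | 10% | 80% |
| 0.3 | 1.20 | 1.966 | 4.9% | 70% |
| 0.5 | 1.41 | 2.326 | 2.0% | 56% |
| 0.7 | 1.83 | 3.003 | 0.3% | 30% |

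Simulation at n = 107 agreed, with levels of 4.6%, 2.0% and 0.3% and power of 68–70%, 55–56% and 29–31%.

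**The case against.** The strongest reply is that this is loose wording and not a lost test. Under reading 1, the closest to the stated outcomes and contrasts, a competent analyst drops the redundant columns and is left with exactly the right test. That stands, and it limits the harm. It does not rescue the sentence, because the coefficient the plan says it will test is not the one that survives.

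Second, the three readings are not exhaustive. The three terms are only those of interest, so child indicators or clustered errors are not excluded, and with raw rows either would give a valid test. First-visit data alone would also be correctly sized, but would discard the deltas and the crossover. This stands too. A reader might infer that no valid test is possible under the plan, and the documents do not support that. Valid versions exist, but the plan does not name one.

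Third, stacking both deltas is a strained reading, since each exposure is stated against control. I agree, and I would not rest the point on reading 2.

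Three further inferences go beyond the documents:
- That false positives are inflated. Under the equal-variance assumptions used here, the errors in readings 2 and 3 are conservative.
- That section 2 (Objectives and Hypotheses) sets a moderation hypothesis for each task. It does not. Its second hypothesis, for example, is that "attentional training that improves sustained attention protects children against attention to peripheral food cues", which concerns the effect of training and not its variation with usual multi-tasking.
- That the median split will mislead because one half may reach significance and the other not. The plan has no rule comparing significance between the halves, so this is not a decision it makes. Equally, the split is not a formal test and cannot replace one.

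**Conclusion.** The point holds as a mis-stated test that should be corrected before analysis. As written, the product term is aliased with usual multi-tasking (one delta per child), compares the tasks with each other (stacked deltas), or has too large a standard error (raw rows without a within-child term).

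The size of the problem depends on the reading. Under the first the cost is a redundant term and an ambiguous report. Under the third it is lost power, from 80% to between 70% and 30% for rho between 0.3 and 0.7, and nothing at rho = 0. The third-reading figures rest on assumed values of rho, equal variances and a benchmark effect set to give 80% power. That the product is aliased in reading 1 and compares the two tasks in reading 2 is algebra and needs none of these assumptions.

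The test is secondary to the task effects, which keeps the point below the most serious class.

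**What to change.** Define delta as task minus control within child, and replace the interaction sentence with:

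> For each outcome and each contrast (multi-task minus control; sustained attention minus control), the within-child delta will be regressed on mean-centred usual media multi-tasking, adjusting for the visit positions of the two conditions. The Wald test of the usual multi-tasking slope at P<0.10 is the interaction test.

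In simulation with an assumed visit effect of 0.3 SD per visit, this regression held its level (9.0% to 10.3%) with 77% to 79% power. Without the visit positions, power was 69% to 74%. Its drawback is that a child drops out of a contrast when either of its two visits is missing.

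An equivalent option is a mixed model with condition (control as reference), visit, usual multi-tasking and condition × usual multi-tasking, testing the two interaction terms separately. The within-child covariance should be unstructured and indexed by condition, and the text must say so. With the multi-task SD 1.5 times larger, indexing by condition gave 9.4% to 10.8% at nominal 10%. Indexing by visit gave 13% to 16% for the multi-task term and 5% to 6% for the sustained-attention term.

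The cost is a change of wording in section 4 and a few lines of code, with no new data or visits.
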